6.3 Tertiary objectives

The following tertiary objectives related to acclimatization and daily-life fatigue are considered exploratory.

- To evaluate daily-life fatigue (via the Need for Recovery scale – NfR questionnaire) with Ponto 4 after field trial compared to own device.
- Relationship between NfR scores and pupil dilation with Ponto 4 after field trial.
- We will investigate in an explorative manner how the overall and peak pupil dilation change between Visit 1-2 (before the field trial) and Visit 3 (after the field trial), for the contrast OSN Auto vs. OSN OFF at +4 dB SNR. Due to the explorative nature of the tertiary objective, no hypothesis is anticipated here.
- We will investigate in an explorative manner how the pupil dilation curve changes between Visit 1-2 (before the field trial) and Visit 3 (after the field trial), for the contrast OSN Auto vs. OSN OFF at +4 dB SNR. Due to the explorative nature of the tertiary objective, no hypothesis is anticipated here.
- We will investigate in an explorative manner how the recognition scores change between Visit 1-2 (before the field trial) and Visit 3 (after the field trial), for the contrast OSN Auto vs. OSN OFF at +4 dB SNR. Due to the explorative nature of the tertiary objective, no hypothesis is anticipated here.
- Relationship between pupil dilation and the patient's PTA and characteristics.
- Relationship between speech recognition scores and the patient's PTA and characteristics.

- Relationship between NfR scores and the patient's PTA and characteristics.

7. DESIGN OF THE CLINICAL INVESTIGATION

This study is a single-center, single-blinded, prospective study on adults BAHS users, who are already experienced Ponto users (see inclusion criteria).

All participants will perform a speech-in-noise test at different SNRs and at three different Ponto 4 settings (OSN ON, OSN OFF, OSN Auto) while an eye-tracking camera records pupil dilation as an indicator of listening effort. The patients are blinded to the test condition. Patients that are bilaterally implanted, will be tested bilaterally with a Ponto 4 placed on each abutment. Patients that are unilaterally implanted will be tested with a Ponto 4 on the implanted side and the opposite ear will remain open and unaided. For the unilaterally fitted patients, no crucial contribution from the opposite side is expected to occur since they also have a hearing loss on the opposite ear (see inclusion criteria). All participants will perform all conditions and will act as their own control.

See Appendix A and B for a list of all conditions and time estimates.

Pupillometry at Visits 1 and 2

The tested conditions will be balanced across participants and across visits (see Figure 1 and Appendix B for the details). The three OSN settings (OSN ON, OSN OFF, OSN Auto) will be tested at the same visit for the same SNR to avoid differences in pupil dilation that could occur across visits (e.g., small differences in camera positioning, lighting, fatigue,...). The order of SNRs will be randomized within each OSN settings (see Figure 1). In a best attempt to maintain motivation constant within and across visits, easy and difficult conditions will be balanced across visits (i.e., SNRs of -8 dB, 0 dB, and +8 dB at one visit; SNRs of -4 dB and +4 dB at the other visit).

Two training lists (+4 dB SNR with OSN OFF, and -4 dB SNR with OSN ON) will be performed before starting the test at Visit 1. Since Visit 2 is scheduled within a week after Visit 1, only one training list will be performed before starting the test at Visit 2.

The setting OSN Auto will only be performed at +4 dB SNR. This SNR was specifically chosen to lead to a speech intelligibility performance, on average, above 50% – hence before the “give up” point, while still activating of the OSN feature. The OSN Auto condition will be tested either at Visit 1 or Visit 2, in between the other two settings (see Figure 1).

Field-trial period

After the first two laboratory visits, the test person will undergo a field trial period of about 3 months, where Ponto 4 will be used in everyday life (with OSN set to Auto) instead of the patient's own Ponto.

Pupillometry at Visit 3

After the field trial period, a third visit will be performed, where the same speech-in-noise test will be carried out at two Ponto 4 settings (OSN Auto and OSN OFF), while an eye-tracking camera records pupil dilation. Two training lists (+4 dB SNR with OSN OFF, and +4 dB SNR with OSN Auto) will be performed before starting the test at Visit 3.

The test leader will change the test devices/programs when required by the test condition (OSN ON, OSN OFF, OSN Auto) and according to the SNR randomization for each patient.

Two questionnaires (SSQ and NfR) will also be completed in relation to the patient's own device (at Visit 1) and in relation to Ponto 4 after 3-months trial (at Visit 3) In addition, the SSQ will also be completed after 1-month trial with Ponto 4. A preference questionnaire will also be completed at Visit 3 to evaluate the preference of Ponto 4 vs. the patient's own device.

Finally, audiology (AC, masked BC) and sound-field thresholds (aided with Ponto 4) will be performed at Visit 3. These audiometric evaluations are performed at Visit 3 instead of Visit 1 to reduce the burden on the participants at Visit 1.

See the detailed study overview in Table 1.

[figure not shown]

Figure 1: Schematic showing the study conditions (SNRs and OSN settings) for pupillometry testing, balanced across patients and visits.

Table 1 Overview of the study visits.

	Visit 1	Visit 2 [1-10 days after visit 1]	Phone reminder [4-5 weeks after visit 2]	Visit 3 [12-15 weeks after visit 2]
Consent form	x			

BC in situ and fitting with Ponto 4	x			
Pupillometry	x	x		x
Field trial with Ponto 4		x (start)		x (end)
Audiometry (AC and masked BC)				x
Sound field audiometry				x (aided with Ponto 4)
SSQ questionnaire	x (reference device)		x (Ponto 4)	x (Ponto 4)
Need of recovery questionnaire (NfR)	x (reference device)			x (Ponto 4)
Preference questionnaire				x

7.1. Endpoints

7.1.1 Primary endpoints

- Difference in overall pupil dilation, as calculated via Growth Curve Analysis, between OSN ON and OSN OFF at +4 dB SNR (conditions measured at visit 1 or 2).

7.1.2 Secondary endpoints

- Difference in peak pupil dilation (PPD) between OSN ON and OSN OFF across SNRs.
- Difference in speech recognition scores between OSN ON and OSN OFF across SNRs.
- Difference in overall pupil dilation, as calculated via Growth Curve Analysis, between OSN ON and OSN OFF across SNRs.
- Difference in overall pupil dilation between OSN Auto and OSN OFF at +4 dB SNR (measured at visits 1 or 2), as calculated via Growth Curve Analysis.
- Difference in overall pupil dilation between OSN Auto and OSN OFF at +4 dB SNR (measured at visit 3), as calculated via Growth Curve Analysis.
- Difference in overall pupil dilation between OSN Auto and OSN ON at +4 dB SNR (measured at visits 1 or 2), as calculated via Growth Curve Analysis.
- Difference in SSQ scores between Ponto 4 after 1 month field trial and own device.
- Difference in SSQ scores between Ponto 4 after 3 months field trial and own device.
- Difference in SSQ scores between Ponto 4 after 1-month field trial and after 3-months field trial.
- Correlation between peak pupil dilation and speech recognition scores.

- Number of test subjects preferring Ponto 4.
- Sound scenarios for which test subjects significantly prefer Ponto 4 over own device.
- Difference in dB between aided thresholds and BC in-situ thresholds –i.e., remaining air-bone gap (also known as BC gain or effective gain).

7.1.3 **Tertiary endpoints**

- Difference in NfR scores with Ponto 4 after field trial and own device.
- Correlation between NfR scores and pupil dilation with Ponto 4 after field trial.
- Difference in overall pupil dilation (intercept term) between Visit 1-2 and Visit 3 for the contrast OSN Auto vs. OSN OFF.
- Difference in peak pupil dilation between Visit 1-2 and Visit 3 for the contrast OSN Auto vs. OSN OFF.
- Difference in the following parameters between Visit 1-2 and Visit 3 for the pupil curves obtained with OSN Auto and OSN OFF: rate of growth/decay (linear term), changes in the rate of growth/decay (quadratic term), and the steepness of the curve around inflection points (cubic term).
- Difference in speech recognition scores between Visit 1-2 and Visit 3 for OSN Auto and OSN OFF.
- Correlation between pupil dilation and the patient's PTA and characteristics (e.g., age, unilateral/bilateral implantation).
- Correlation between speech recognition scores and the patient's PTA and characteristics (e.g., age, unilateral/bilateral implantation).
- Correlation between NfR scores and the patient's PTA and characteristics (e.g., age, unilateral/bilateral implantation).

7.2. Outcome measures

7.2.1 **Test subject characteristics**

The following patient characteristics will be recorded:

- Gender (Female, Male, No answer)
- Age
- Unilateral or bilateral BAHS surgery and side
- Date of first BAHS fitting on abutment (year)
- Name of current bone anchored sound processor
- Date of first fitting with current own bone anchored sound processor ([mm/yy])
- History of eye surgery (if any, which eye and year)
- Dominant or preferred eye (Left, Right, None, Not known)
- Job at visit 1 and 3, and whether it is the same.

7.2.2 Primary outcome measures

- Overall pupil dilation for OSN ON and OSN OFF at +4 dB SNR (intercepts obtained from Growth Curve Analysis).

7.2.3 Secondary outcome measures

- Pupil dilation.
- Growth Curve Analysis parameters.
- Speech recognition scores.
- SSQ questionnaire scores.
- Preference questionnaire scores.
- Aided sound field thresholds.
- BC in situ thresholds.

7.2.4 Tertiary outcome measures

- Pupil dilation.
- Growth Curve Analysis parameters.
- Speech recognition scores.
- Need for Recovery (NfR) questionnaire scores.
- BC in situ thresholds (PTA).
- Patient's characteristics.

7.3. Investigational device(s) and comparators

This is a post market study and the devices used in this study are CE marked. The test subjects' own devices will only be used as a reference device for the questionnaires (SSQ, NfR, preference). For the laboratory testing and for the field-trial period, Ponto 4 sound processors will be used. The following devices (and item numbers) will be used:

Name	Amount	Part number (color)	Description
Ponto 4	60	186777 (CBE) 186778 (TC) 186779 (SIL) 186780 (STG) 186781 (CNB) 186782 (DBL)	Oticon Medical BAHS Sound Processor. Released in 2019.

7.3.1. Concomitant treatment and medication

Medication which is considered necessary for the patient's safety and well-being may be given at the discretion of the investigator. Only medication for adverse events must be recorded in the

appropriate section of the Case Report Form (CRF).

7.4 Subject population

Based on the sample size calculation reported in Sec. 12, it was decided that a total of 30 patients will be included in the study. The patients will be selected from the Queen Elizabeth Hospital database. A member of the clinical team at the hospital will perform a pre-screening by looking at the patient's journal, according to the inclusion criteria listed below. It was decided to include preferably patients that are entitled for a sound processor upgrade to reduce the burden on the patient, since patients entitled for an upgrade would need to visit the clinic anyways to get a new sound processor fitted. Only the patients that fulfil those inclusion and exclusion criteria that are available on the patient's journal will be contacted and considered suitable candidates for the study. Screening will occur at Visit 1 after the informed consent is signed. Patients that fulfil all inclusion and exclusion criteria will be enrolled in the study.

Inclusion criteria

- Minimum 18 years and maximum 70 years old.
- UK English mother tongue.
- Bilateral conductive or mixed hearing loss.
- Users fitted unilaterally or bilaterally on abutment.
- Users are currently fitted with either Ponto 3, Ponto Plus or Ponto Pro (devices with a fitting range up to 45 dB HL).
- Users with at least 6 months of daily experience with one Ponto sound processor.
- BC thresholds of the implanted ear(s) better (lower) than or equal to 40 dB HL (average of 0.5, 1, 2 and 3 kHz) based on BC in-situ measurement at the first visit.
- People currently employed/self-employed (since the Need for Recovery questionnaire refers to work-related fatigue).
- Speech recognition scores better (higher) than or equal to 50% at +4 dB SNR with OSN OFF (as assessed via the first training list at Visit 1). This is to avoid including patients that are already “giving up” at +4 dB SNR.
- Users entitled for a sound-processor upgrade (according to the investigator) will first be selected. If there are not enough users entitled for an upgrade, then patients fitted with Ponto between 7 and 12 months before visit 1 will be considered. If there are not enough users within 7-12 months, then patients fitted with Ponto between 13 and 18 months before visit 1 will be considered.

Exclusion criteria

- Single-sided deafness (SSD)
- Hearing aid or cochlear implant on the opposite ear.
- Test persons with current eye diseases and/or history of eye surgery on both eyes.
- If the patient takes medications that can impact the autonomic nervous system – and hence pupil dilation (e.g., drugs for Parkinson's disease, peptic ulcers, incontinence, motion sickness; Winn et al. (2018)).
- If the investigator or physician assesses that the patient is not fit for trial participation.

Please note that if a patient has taken any caffeine (e.g., coffee, tea, energy drink, other) in the 6 hours preceding testing, the visit should be rescheduled.

Criteria for early termination during the study

- System not being able to track pupil dilation (e.g., technical failure, eye iris color, other).
- Noisy pupil recordings (e.g., too many eye blinks, elevated baseline, not possible to individuate a clear peak dilation because of an event-unrelated dilation occurring at baseline, ..).
- If the patient cannot remove (or is uncomfortable to be tested without) glasses or contact lenses during pupillometry and the system cannot track the pupil reliably.
- Inability to complete the speech-in-noise test.
- Patient who switch to non-Ponto sound processor during the field-trial period.
- Patients who do not want to continue to participate.
- If the patient start taking medications that can impact the autonomic nervous system – and hence pupil dilation (e.g., drugs for Parkinson's disease, peptic ulcers, incontinence, motion sickness; Winn et al. (2018)).
- If the test leader or physician assesses that the patient is not fit for trial participation at any stage.

If a patient is excluded or early terminated from the study or decides to withdraw from the study, the patient will continue to receive care from the physician following the clinical practice guidelines of the hospital.

Procedure for replacement of subjects

If test persons are withdrawn from the study, the recruitment process will continue until 30 patients have completed Visit 1 and Visit 2. Dropouts will be replaced during the study by enrolling new test participants.

Time frame for the study

The study is a 4 months study, i.e. 4 months is the total time a patient is enrolled in the study. The second visit is expected to be performed within maximum 10 days after Visit 1. The second visit cannot be performed on the same day as Visit 1. Hence, the time window for Visit 2 is 1-10 days after Visit 1. The third visit is expected to be performed 3 months after Visit 2. The time window for Visit 3 is 12-15 weeks after Visit 2 to allow for investigation of acclimatization.

The data after completion of the first two visits may be analyzed and reported if the investigator finds this appropriate. Interim data analysis will be performed in November 2019 to be able to present interim results at the OSSEO conference in December 2019.

Enrollment will start after receiving Ethical approval and will be ongoing until the total number of patients (see Sec. 12) has been reached. This is expected to be fulfilled by the end of January 2020. The end of the study is therefore expected to occur by the end of May 2020.

After the study, the patient will be receiving follow-up according to the clinic's standard procedures for patients with BAHS.

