8. STUDY PROCEDURES

8.1. Investigation outline

Each test person will participate in three lab visits and a field-trial period.

Pre-screening

Adult patients who are already implanted with a BAHS are considered candidates for the study (see inclusion criteria).

- The audiologist will pre-screen the database for suitable candidates that meet the inclusion criteria.
- The test person is contacted over the phone or through an email or letter.
- The test person is informed about the study.
- The test person is given time to consider his/her participation and ask questions.
- The test person is given the opportunity to either accept or decline the offer to participate in the study.
- If a test person accepts, the 1st visit is scheduled. The patient is reminded that no caffeine should be taken on the 6 hours before Visit 1.

Visit 1

- The test person is informed about the study including all study related visits.
- Detailed information and instructions about the study.
- Consent form is signed.
- The test person's demographical data as well as their personal data and patients' characteristics are registered in the CRF.
- Fitting of Ponto 4 is performed (OSN ON, OSN OFF, OSN Auto)
- Pupillometry during a speech-in-noise test is performed (training, OSN ON, OSN OFF, OSN Auto – see Figure 1).
- All subjects fill in the SSQ and NfR questionnaires in relation to their own device (reference device).

Visit 2: 1-10 days after Visit 1

- Get Ponto 4 ready for testing (OSN ON, OSN OFF, OSN Auto)
- Pupillometry during a speech-in-noise test is performed (training, OSN ON, OSN OFF, OSN Auto – see Figure 1).
- The test person is instructed on the usage of Ponto 4 (including getting the Oticon ON app on their smartphone, or offer a Connectclip)
- SSQ questionnaire is handed out.

Phone reminder: 4-5 weeks after Visit 2

- The test leader reminds the patient to fill out the SSQ questionnaire in relation to the performance with Ponto 4 in the first month of trial. The patient will then put the questionnaire in an envelope and bring it at Visit 3.

Visit 3: 12-15 weeks after Visit 2

- Hand in SSQ questionnaire filled out at home.
- Pupillometry during a speech-in-noise test is performed (training, OSN OFF, OSN Auto).
- Audiometry is performed (AC, masked BC).
- Sound-field audiometry is performed with Ponto 4.
- All subjects fill in the SSQ and NFR questionnaires in relation to Ponto 4.
- All subjects fill in the preference questionnaire.

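### Section 7.4 makes pupil-signal problems grounds for ending the whole study, so a patient who first meets one after Visit 2 may not give Visit 3 data that need no pupil trace

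*Combined protocol and SAP*

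**What the plan says.** Section 7.4 has a list titled "Criteria for early termination during the study". Four of its entries concern the pupil signal:

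- "System not being able to track pupil dilation (e.g., technical failure, eye iris color, other"
- "Noisy pupil recordings (e.g., too many eye blinks, elevated baseline", with further examples
- glasses or contact lenses that the patient cannot do without "during pupillometry and the system cannot track the pupil reliably"
- "If the patient start taking medications that can impact the autonomic nervous system – and hence pupil dilation"

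None is tied to a particular visit. The only stated consequence of termination is that the patient goes on receiving the hospital's usual care. No section provides for stopping pupillometry while the patient stays in for the other assessments.

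On replacement, section 7.4 says that "the recruitment process will continue until 30 patients have completed Visit 1 and Visit 2", and section 12.1 repeats this target. The next sentence of 7.4 adds, without a visit limit, that dropouts will be replaced by new participants.

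For Visit 3, section 8.1 lists the return of the 1-month SSQ first. Next comes "Pupillometry during a speech-in-noise test is performed (training, OSN OFF, OSN Auto". After that come audiometry, aided sound-field thresholds, the SSQ and NfR for Ponto 4, and the preference questionnaire.

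**The concern.** The four criteria protect the validity of the pupil recording. The drug criterion gives pupil dilation as its reason, and section 5 expects no interaction between the study treatment and other medication. The first criterion even covers an equipment fault. Yet the stated consequence falls on the whole of the patient's participation.

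After Visit 2 this brings no benefit to the primary endpoint, which has already been measured. What is at stake is the 3-month follow-up: self-reported hearing, work-related fatigue, preference and aided thresholds, from a patient who may have worn the device for the full field trial. Section 7.4 treats another threat to the pupil signal more lightly: recent caffeine leads to a rescheduled visit.

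**Working it through.** **1. Which endpoints are exposed.** Section 7.1.2 has 13 secondary endpoints. Those that need no pupil trace but depend on Visit 3 (Table 1 and section 8.1) are:

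| Secondary endpoint | Termination before Visit 3 | New recording failure at Visit 3 |
|---|---|---|
| SSQ, 1 month vs own device | at risk | not at risk (handed in before pupillometry) |
| SSQ, 3 months vs own device | at risk | at risk |
| SSQ, 1 vs 3 months | at risk | at risk |
| Number preferring Ponto 4 | at risk | at risk |
| Scenarios in which Ponto 4 is preferred | at risk | at risk |
| Aided minus BC in-situ thresholds | at risk | at risk |

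That is 6 of 13 in the first case and 5 of 13 in the second. Two tertiary endpoints are also exposed: the NfR difference, since the Ponto 4 NfR is collected only at Visit 3, and the change in speech scores, where the sentence test could still have been done. The primary endpoint (7.1.1) is measured at Visit 1 or 2 and is not exposed.

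**2. Which patients are exposed.** Iris colour, frequent blinking and dependence on glasses are largely stable. They should mostly show during the 11 test lists of Visits 1 and 2 (Appendix B: 6 + 5), and patients lost at that stage are replaced. The exposed group is mainly those who start a listed drug during the field trial and those with a new recording failure at Visit 3.

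**3. Whether replacement covers them.** The numerical target is met once 30 patients complete Visits 1 and 2, so a later loss does not reopen it. The sentence on replacing dropouts could be read as covering later losses. The timetable limits that reading. Section 7.4 expects enrolment to finish by the end of January 2020 and the study to end by the end of May 2020. Visit 3 falls at least 12 weeks (84 days) after Visit 2. Counting back 84 days from 31 May gives 8 March, so a replacement who completes Visit 2 after about that date cannot finish on schedule.

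**4. Size.** The plan gives no rate of late pupil failure and no precision target for these endpoints. Its one sample-size figure, 29, is for the primary endpoint. It reproduces with a paired t-test at effect size 0.48, one-sided 5% and 80% power (power 0.810 at n = 29), and it does not bear on this point.

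The loss counts below are therefore assumptions. Inputs: 30 patients complete Visit 2, k of them are lost, n = 30 − k, and the standard deviation of the paired difference is unchanged. The standard-error ratio is sqrt(30/n). The detectable standardized paired effect is for 80% power, two-sided 5%, noncentral t.

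| k | n | sqrt(30/n) | Rise in standard error | Detectable effect |
|---|---|---|---|---|
| 0 | 30 | 1.000 | 0% | 0.53 |
| 1 | 29 | 1.017 | 2% | 0.54 |
| 3 | 27 | 1.054 | 5% | 0.56 |
| 6 | 24 | 1.118 | 12% | 0.60 |

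The ratio applies directly to NfR (paired test) and to the mean aided-minus-in-situ difference. For SSQ, section 12 plans a mixed-model ANOVA. If that model keeps incomplete cases, a patient with own-device and 1-month scores still contributes, and the loss is smaller than tabulated.

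**The case against.** The strongest reply is that the plan never says valid data are thrown away. A reader might infer that the trial discards 3-month data, and the documents do not support that. Section 7.4 says only that usual care continues. Section 12 restricts the final analysis to patients who completed Visits 1 and 2, a condition that someone terminated later still meets. Section 8.1 has all subjects completing the Visit 3 questionnaires. All of this stands. What remains is that a patient terminated from the study is not clearly among the subjects expected to complete Visit 3, and no text says that such a patient continues. The loss lies in data not collected.

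Three other strong inferences also fail. A camera failure at Visit 3 does not cost the 1-month SSQ, which is handed in first. Later losses cannot be said to go unreplaced, because the sentence on dropouts leaves that open. Nor would every loss be avoided by a change of wording, since some of these patients might not attend Visit 3 anyway.

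It is also fair to say that this is a pupillometry study, that the exposed endpoints are secondary or exploratory, and that the number affected may be nil. That bears on priority. It does not supply a reason for ending non-pupil assessments on pupil grounds.

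**Conclusion.** The point holds in limited form. Read literally, section 7.4 ends study participation for a problem confined to the pupil signal, including one that first arises after Visit 2. The patient's remaining Visit 3 assessments are then forgone or, at best, left undefined.

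The effect on precision is modest: nil to 2% for no loss or one loss, and 12% for an assumed six. These figures rest on assumed counts, complete-pair analysis and an unchanged standard deviation. The conclusion that the rule should be split does not depend on the counts, because ending the other assessments brings no gain to the primary endpoint, and invalid Visit 3 pupil recordings can be excluded by themselves. This is a low-cost improvement to the secondary and tertiary results and does not call the primary analysis into question.

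**What to change.** In section 7.4, state that when any of the four pupil-signal criteria is first met after Visit 2 is complete, the affected pupil recordings are excluded or pupillometry is stopped. The patient then continues to Visit 3 for SSQ, NfR, preference, audiometry and aided thresholds, and for speech scores where the sentence test can still be done.

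Leave every other termination criterion as it is: the switch to a non-Ponto processor, inability to complete the speech test, withdrawal, and the judgement that the patient is unfit to take part. The processor-switch criterion matters here because it protects the meaning of the 3-month Ponto 4 ratings. Leave terminations before the end of Visit 2, and their replacement, as planned. The change concerns data collection only and says nothing about medication or clinical care.

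Add a CRF entry for pupil-data validity (yes or no, with reason), and report the number analysed for each endpoint. The cost is the wording and that entry, with no extra visit, device or staff. The drawback is that the number analysed will differ between endpoints.
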